### Secondary outcomes:

The difference in change from baseline between *B. breve* and placebo in:

1. Body composition (weight, BMI, android/gynoid fat ratio, and muscle mass (% or g) as assessed by DXA after 12 weeks of supplementation
2. Waist circumference, hip circumference, and waist/hip circumference ratio after 6 and 12 weeks of supplementation
3. Lipid profile (total cholesterol, HDL-cholesterol, LDL-cholesterol, triglycerides) after 12 weeks of supplementation
4. Biomarkers of glycemic control (fasting blood glucose, HbA1c, fasting insulin levels) after 12 weeks of supplementation
5. Liver markers (aspartate transaminase (AST), alanine aminotransferase (ALT), gamma-glutamyl transferase (GGT), and alkaline phosphatase (ALP)) after 12 weeks of supplementation
6. Frequency of bowel movements after 6 and 12 weeks of supplementation
7. Body composition (weight, BMI, total body fat (% or g), android fat (% or g), gynoid fat (% or g), android/gynoid fat ratio, and muscle mass (% or g) and waist circumference, hip circumference, and waist/hip circumference ratio) in participant groups classified by microbiota composition at week 0
8. Microbiota composition analysis

### Safety outcomes:

[figure not shown]
1. Incidence of pre-emergent and post-emergent adverse events

2. Vital signs (blood pressure (BP) and heart rate (HR)), respiratory rate, and temperature
3. Clinical chemistry (total bilirubin, creatinine, blood urea nitrogen (BUN), Na, K, Cl, Ca, Fe, Mg, phosphate, and estimated glomerular filtration rate (eGFR))
4. Hematology (white blood cell (WBC) count with differential (neutrophils, lymphocytes, monocytes, eosinophils, basophils), red blood cell (RBC) count, hemoglobin, hematocrit, platelet count, RBC indices (mean corpuscular volume (MCV), mean corpuscular hemoglobin (MCH), mean corpuscular hemoglobin concentration (MCHC), red cell distribution width (RDW), and mean platelet volume (MPV))
5. Urinalysis (microscopy, glucose, ketones, specific gravity, blood, protein, nitrite, leukocytes, colour, appearance urobilinogen/urine bilirubin, urine pH)

### Exploratory analyses

1. Total body fat (%) change during the run-in period as assessed by bioelectrical impedance analysis (BIA)
2. Comparison of total body fat (%) as assessed by BIA and DXA at baseline

## 6 STUDY DESIGN

This study will be conducted at the KGK Science clinic in London, ON.

The planned sample size for this study is 100 healthy adults. To evaluate primary, secondary, and safety outcomes, study assessments will be conducted as per the Schedule of Assessments in Section 1.3.

Study Arm	Number of Participants
B. breve	N = 50
Placebo	N = 50
Total	N = 100

## 7 SELECTION OF STUDY POPULATION

This study will enroll 100 healthy male and/or female adults. Each participant must fulfill the inclusion criteria and not meet any of the exclusion criteria as described in Sections 7.1 and 7.2, respectively.

### 7.1 Inclusion Criteria

1. Male or female between 20 and 65 years of age, inclusive
2. BMI from 25.0 to 29.9 kg/m^2, inclusive
3. Female participants are not of child-bearing potential, defined as females who have undergone a sterilization procedure (e.g. hysterectomy, bilateral oophorectomy, bilateral tubal ligation, complete endometrial ablation) or have been post-menopausal (natural or surgically) for at least 1 year prior to screening

Or,

## Protocol 20BWHM:

A randomized, double-blind, placebo-controlled study to investigate the effects of a *Bifidobacterium breve* strain on fat loss in healthy adults

Females of child-bearing potential must have a negative baseline urine pregnancy test and agree to use a medically approved method of birth control for the duration of the study. All hormonal birth control must have been in use for a minimum of three months. Acceptable methods of birth control include:

- Hormonal contraceptives including oral contraceptives, hormone birth control patch (Ortho Evra), vaginal contraceptive ring (NuvaRing), injectable contraceptives (Depo-Provera, Lunelle), or hormone implant (Norplant System)
- Double-barrier method
- Intrauterine devices
- Non-heterosexual lifestyle or agrees to use contraception if planning on changing to heterosexual partner(s)
- Vasectomy of partner at least 6 months prior to screening

4. Self-reported stable body weight for the past 3 months defined as not having gained or lost more than 5 kg of body weight throughout the 3 months prior to baseline
5. Participants with the following body fat percentages:
  - Female:  $\geq 25\%$  as determined by Bioelectrical Impedance Analysis (BIA) at screening and confirmed  $\geq 30\%$  by Dual-Energy X-Ray Absorptiometry (DXA) at baseline
  - Male:  $\geq 15\%$  as determined by BIA at screening and confirmed  $\geq 20\%$  by DXA at baseline
6. Agrees to follow the diet and exercise guidelines for the duration of the study
7. Willingness to complete questionnaires, records, and diaries associated with the study, to complete all clinic visits, and provide stool samples
8. Provide voluntary, written, informed consent to participate in the study
9. Healthy as determined by medical history, laboratory results and physical exam as assessed by the Qualified Investigator (QI)

## 7.2 Exclusion Criteria

1. Women who are pregnant, breastfeeding or planning to become pregnant during the trial
2. Allergy, sensitivity, or intolerance to the investigational product's active or inactive ingredients
3. Clinically significant abnormal laboratory results at screening as assessed by the QI
4. Current or history of any significant gastrointestinal disease requiring medication (e.g. GERD, gastroenteritis)
5. Irregular sleep schedule
6. Chronic diarrhea or constipation
7. Participants with hypertension and are on antihypertensive medication
8. Type I or Type II diabetes
9. Participants with hyperlipidemia and are on medication
10. Self-reported sleep apnea
11. Self-reported current or pre-existing thyroid condition. Treatment on a stable dose of medication for at least 3 months will be considered by the QI
12. Unstable metabolic disease or chronic diseases as assessed by the QI
13. History of or current diagnosis with kidney and/or liver diseases as assessed by the QI on a case-by-case basis, with the exception of history of kidney stones in participants who are symptom-free for 6 months

14. Significant cardiovascular event in the past 6 months. Participants with no significant cardiovascular event on stable medication may be included after assessment by the QI on a case by case basis
15. Major surgery in the past 3 months or individuals who have planned surgery during the trial period. Participants with minor surgery will be considered on a case-by-case basis by the QI
16. Cancer, except skin cancers completely excised with no chemotherapy or radiation with a follow up that is negative. Volunteers with cancer in full remission for more than five years after diagnosis are acceptable
17. Individuals with an autoimmune disease or are immune-compromised
18. Self-reported HIV-, Hepatitis B- and/or C-positive diagnosis
19. Blood/bleeding disorders as determined by laboratory results
20. Self-reported mental or neuropsychological condition and/or cognitive impairment that, in the QI's opinion, could interfere with study participation
21. Metal implants that may affect the DXA scan results will be assessed on a case-by-case basis by the QI.
22. Current use of prescribed medications listed in Section Prescribed Medications 7.3.1
23. Current use of over-the-counter medications, supplements, foods and/or drinks listed in Section 7.3.2
24. Use of cannabinoid products within 60 days of baseline. History of cannabis used will be assessed on a case by case basis by the QI
25. Use of tobacco products within 60 days of baseline
26. Self-reported alcohol or drug abuse within the last 12 months
27. High alcohol intake (average of > 2 standard drinks per day or > 10 per week)
28. Current employment that calls for shift work or have worked shift work in the last 3 weeks
29. Participation in other clinical research trials 30 days prior to screening
30. Blood donation 30 days prior to screening, during the study, or a planned donation within 30-days of the last study visit
31. Individuals who are unable to give informed consent
32. Any other condition, that, in the opinion of the QI, may adversely affect the participant's ability to complete the study or its measures, or which may pose a significant risk to the participant

### 7.3 Concomitant Medications

Participants who are taking any prescribed medications that are considered not to affect the study outcomes must agree to maintain their current dosing regimen during the study unless otherwise recommended by their family physician.

#### 7.3.1 Prescribed Medications

Participants on the following prescribed medications and/or treatments will be excluded during enrollment unless they have been taken off these therapies by their family physician. In the latter event, the frequency of use and/or dosage may be considered by the QI on a case by case basis prior to recommending an appropriate washout or their enrollment in the study.

1. Beta-blockers and thiazide diuretics (within 4 weeks of baseline)
2. Weight loss medication (within 4 weeks of baseline)
3. Lipid-lowering medications (within 4 weeks of baseline)
4. Anticoagulants and coagulants (within 4 weeks of baseline)
5. Sleep medication
6. Selective serotonin reuptake inhibitors (SSRI)
7. Antibiotics
8. Non-steroidal anti-inflammatory drugs (NSAIDs)
9. Proton pump inhibitors (PPIs)
10. Metformin (unless on a stable dose for the last 6 months)

### 7.3.2 Over-the-counter Medications, Supplements and Foods/Drinks

Participants who are currently consuming the following over-the-counter (OTC) medications, supplement, and food/drinks will not be allowed to participate unless willing to undergo the specified washout period prior to their baseline visit and agree not to take the supplements during the study. Other OTCs supplement and food/drinks will require a case-by-case assessment by the QI based on dose and/or frequency of use to determine adequate washout.

1. Probiotics, prebiotics, and synbiotics (30 days prior to baseline and throughout the study) (see appendix 17.1 for full lists)
2. OTC NSAIDs (PRN use is acceptable)
3. OTC blood pressure medication or supplements (within 4 weeks of baseline)
4. Lipid metabolising supplements (within 4 weeks of baseline)
  - a. Fish oil and omega-3 supplements
  - b. Red yeast rice
  - c. Plant sterols and stanols
5. OTC medication or supplements marketed for weight loss (within 4 weeks of baseline)
6. Vitamin E supplements (within 4 weeks of baseline)
7. Coagulant/anticoagulant supplements (within 4 weeks of baseline)
8. PPIs

### 7.4 Washout Periods

Please refer to section 7.3.2 for washout periods for OTC medications, supplements and drinks.

### 7.5 Early Withdrawal

#### *Personal reasons*

As stated in the Informed Consent Form, a participant may withdraw from the study for any reason at any time.

#### *Removal by Qualified Investigator*

Protocol 20BWHM:

A randomized, double-blind, placebo-controlled study to investigate the effects of a *Bifidobacterium breve* strain on fat loss in healthy adults

Participant discontinuation should be considered at the discretion of the qualified investigator. The circumstances of any discontinuation must be documented in detail in the participant file and final report. If possible, the evaluations planned for the end of treatment will be carried out at the time when the participant is withdrawn from the study.

Criteria for removal of participants from the study includes:

*Clinical reasons*

A participant may be withdrawn from the study if, in the opinion of the qualified investigator, it is not in the participant's best interest to continue. Any participant who experiences a serious adverse event (SAE) may be withdrawn from the trial at the discretion of the qualified investigator. A participant will also be withdrawn due to adverse events causing clinically significant illness or the need for prohibited medication(s) during the trial. Any female participant who becomes pregnant during the course of the trial will be withdrawn and will be followed up until giving birth.

*Protocol violation*

Any participant found to have entered this study in violation of the protocol will be discontinued from the study at the discretion of the qualified investigator. This will include any participant found to have been inappropriately enrolled (did not meet eligibility criteria). Participant non-compliance includes failure to show up for study visits, failure to take the investigational product as directed, or refusal to undergo study visit procedures. Participants who are found to be taking prohibited medications or supplements without the knowledge of the qualified investigator will also be withdrawn. Any major protocol deviations (i.e. those that increase the risk to participants and/or compromise the integrity of the study or its results) will result in participant discontinuation.

*Participapnt Replacement*

For all early withdrawals, a participant leaving the study prematurely or in the event of participant removal will NOT be replaced by another. It is understood by all concerned that an excessive rate of withdrawals can render the study un-interpretable, thus unnecessary withdrawal of participants should be avoided.

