## **9.6 Visit 4 - End of Study (Week 12, 84 ± 3 days)**

Participants will return to the clinic fasted for 12 hours or greater with the unused product, in addition to completed subject diaries, food records, daily bowel habits diaries, exercise diaries, and stool collections, for assessments. Compliance calls will be made at fixed intervals.

Visit 4 assessments include:

1. Review concomitant therapies and adverse events
2. Return the unused investigational product in the original packaging and remnants; calculate compliance
3. Collect and store stool samples
4. Collect and review Subject Diary
5. Collect and review 3DFR
6. Collect and review Daily Bowel Habits Diary
7. Collect and review Exercise Diary
8. Urine collection
  - a. Urinalysis (microscopy, chemical, urobilinogen/urine bilirubin)
9. Seated resting blood pressure, heart rate, respiratory rate, and temperature measurements
10. Weight (BMI calculation), waist and hip circumference measurements (waist/hip circumference ratio)
11. Collect fasted blood samples for analysis of CBC, Na, K, Cl, Fe, Mg, Ca, phosphate, HbA1c, fasting glucose, eGFR, creatinine, BUN, AST, ALT, GGT, ALP, total bilirubin, lipid profile, and fasting insulin
12. DXA scan

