## **10.8 Dual-Energy X-Ray Absorptiometry (DXA) Scan**

The Dual-Energy X-Ray Absorptiometry Scan will be conducted at KGK clinic (London, ON) at visits 2 (week 0), and 4 (week 12) by trained technicians. Body tissue density will be measured by a form of X-ray radiation and converted into body fat and muscle mass percentage for assessment. Prior to the day of the DXA assessment, the coordinators will remind the participants to limit the amount of water and food consumption accordingly. A full body composition DXA scan will expose the participant to a total dose of <10uSV, depending on the size of the participant. This amount is less than a person is exposed to on an east to west coast flight within the USA and similar to the normal background radiation received over the course of a single day level (23, 24).

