## 12 STATISTICAL EVALUATION

### 12.1 Determination of Sample Size

With a total sample size of 100 (50 per group; 40 completers), it is possible to detect a difference in mean change in percent body fat or body fat mass of 0.76% or 0.79 kg respectively, in a parallel design at a two-sided unadjusted 5% significance level, 80% power and 20% attrition rate. This calculation is based on standard deviations of 1.19% and 1.24 kg for percent body fat and body fat mass respectively, estimated from a study by Minami et al (2018).

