## 5. EFFECTIVENESS/ EFFICACY ANALYSIS

### 5.1 Primary outcomes

Primary Outcomes	Hypothesis
1- The difference in change in fat loss from baseline (% or g), as assessed by DXA, between B. breve and placebo after 12 weeks of supplementation.	H0: There is no difference in mean change in fat loss, as assessed by DXA, from baseline at week 12 between B. breve and placebo

Summary statistics including number of participants, mean, median, standard deviation, minimum, and maximum will be obtained for baseline and week 12 visits. Similar summary statistics will be obtained for the change from baseline to week 12. Mean values will be displayed as graphs, with a separate line for each product, and error bars indicating  $\pm$  SEM. Mean changes from baseline will also be graphed similarly.

The primary outcome will be assessed using ANCOVA, with the baseline measurements as covariate and group as the factor variable. The dependent variable will be the change from baseline at week 12. Q-Q plots and residuals versus fitted values plots will be generated for the evaluation of the model adequacy. If the residual plots show violation of the model assumptions, log or other transformation of the dependent variable will be performed.

Between group differences will be assessed by two-sample t- test. If the outcome is not normally distributed, then Wilcoxon rank sum test will be used.

Within group differences will be assessed by paired t-test if the outcome is normally distributed and Wilcoxon signed rank test otherwise. P-values and 95% confidence intervals will be calculated.

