## 7. MISSING DATA

All missing efficacy/effectiveness values analysis will be imputed using the most recent previously available value (LOCF, or “last-observation-carried-forward” imputation) or multiple imputation. No imputation techniques will be performed for missing values of safety variables.

Lab measurements that are below or above the threshold of quantification, will be imputed with that threshold value.

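### An early-withdrawal DXA scan has no stated place in the week-12 primary analysis, and under the LOCF option it becomes the week-12 value whatever week it was taken

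*Protocol*

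**What the plan says.** Protocol 7.5, under removal by the qualified investigator, provides for an exit assessment: "If possible, the evaluations planned for the end of treatment will be carried out at the time when the participant is withdrawn". Protocol 9.6 lists a DXA scan among the Visit 4 assessments, so the exit assessment includes one. Visit 4 has a window of 84 ± 3 days. Protocol 10.8 places DXA "at visits 2 (week 0), and 4 (week 12) by trained technicians", so an exit scan would be a leaver's only DXA after baseline, and no interim visit exists to hold it.

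SAP 5.1 defines the primary analysis: "The primary outcome will be assessed using ANCOVA, with the baseline measurements as covariate and group as the factor variable". It adds: "The dependent variable will be the change from baseline at week 12".

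SAP 7 covers missing efficacy data: "All missing efficacy/effectiveness values analysis will be imputed using the most recent previously available value". The same sentence then offers multiple imputation as an alternative and does not choose between the two.

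SAP 3 admits to the ITT population any treated participant with any efficacy information after randomization, so an exit scan qualifies. The per-protocol population requires completion of all visits. Neither population is named as primary.

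Protocol 11.2.2 describes a different path. After participant-initiated withdrawal or a clinically significant unexplained laboratory abnormality, the participant stops treatment but stays in the study and attends the remaining visits.

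**The concern.** The protocol plans to collect a scan at exit, but neither document says what the analysis does with it. A scan at week 2 or week 5 reflects a short exposure, whereas the endpoint is a 12-week change. Under LOCF the short-exposure value is carried to week 12. Under multiple imputation, the statistician must decide at analysis whether the exit scan is used, ignored or treated as Visit 4.

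The estimate could then mix 12-week changes with changes over shorter, unequal periods. Both arms also exercise throughout, so a difference between arms in the number or timing of exits can itself alter the treatment contrast.

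Early exits are expected. The sample size allows for 20% attrition. Protocol 10.12 withdraws anyone below 70% exercise compliance for two consecutive weeks, and two of three sessions is 67%. Such a participant could leave within the first few weeks and could still be scanned.

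The same gap affects the laboratory values, weight and circumferences measured at exit.

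**Working it through.** **Inputs from Protocol 12.1.** 50 per arm, 40 completers per arm, SD 1.24 kg (or 1.19 percentage points), difference 0.79 kg (or 0.76 points), and "two-sided unadjusted 5% significance level, 80% power and 20% attrition rate".

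**Reproducing the plan's figure.** For a two-sample t-test with 40 per arm, the noncentrality is 0.79 / (1.24 × √(2/40)) = 2.85 on 78 degrees of freedom, which gives power of 80.3%. For 0.76 points with SD 1.19 it is 80.5%. The stated sample size is confirmed. I use a two-sample comparison because the documents give no correlation between baseline and change.

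**Balanced exits, exit scan used as week 12.** Assumptions not in the documents: 20% of each arm leaves, every leaver is scanned, the effect builds linearly over 12 weeks, and the SD is unchanged.

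Estimate = 0.79 × [0.8 + 0.2 × (mean exit week / 12)], with power from the noncentral t at 50 per arm.

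| Mean exit week | Factor | Estimate (kg) | Power |
|---|---|---|---|
| 2 | 0.833 | 0.66 | 75% |
| 4 | 0.867 | 0.68 | 78% |
| 6 | 0.900 | 0.71 | 81% |
| 9 | 0.950 | 0.75 | 85% |

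Dilution is therefore 5% to 17%. The power to compare with is the plan's 80% on 40 completers per arm. Power is about the same or higher for mean exit at week 6 or later, because the leavers add to the number analysed. It falls below the benchmark only for the earlier exits.

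**Unequal exits.** Further assumptions: a shared exercise loss of 1 kg over 12 weeks in both arms, so the true 12-week changes are −1.79 kg (B. breve) and −1.00 kg (placebo), and exits at week 6. Each leaver then shows half the 12-week change.

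- Exits 10% B. breve, 30% placebo: 1.79 × (1 − 0.10 × 0.5) − 1.00 × (1 − 0.30 × 0.5) = 1.70 − 0.85 = 0.85 kg.
- Exits 30% B. breve, 10% placebo: 1.79 × 0.85 − 1.00 × 0.95 = 1.52 − 0.95 = 0.57 kg.

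Against a true 0.79 kg, the errors are +0.06 and −0.22 kg. The standard error with 50 per arm is 1.24 × √(2/50) = 0.25 kg.

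**Leaver without a usable exit scan, under LOCF.** The last DXA value is baseline, so the change is zero. With balanced 20% exits the estimate is 0.8 × 0.79 = 0.63 kg, a 20% dilution. This is larger than any figure in the table, and it limits what a fix can safely say.

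**The case against.** **The plan already ties the endpoint to week 12.** A reader might infer that an exit scan could be filed as the end-of-treatment evaluation, so that the participant is not missing and no imputation rule applies. The documents do not support that. SAP 5.1 specifies week 12 and Visit 4 has a window of 84 ± 3 days, so on a plain reading a week-2 scan leaves week 12 missing and SAP 7 applies. Mis-entry is possible but is not what the plan says. The point therefore rests on SAP 7.

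**Multiple imputation is already permitted.** This is true. But LOCF is equally permitted, and the text does not say how an exit scan would enter the imputation.

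**Not every leaver will have an exit scan.** Scans are done only where possible, and the grounds for removal include missed visits and refused procedures. Protocol 11.2.2 would take some leavers through to a real week-12 scan. This stands, and it makes the figures an upper bound on what exit scans contribute.

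**The direction is not fixed.** A reader might infer that exit scans always pull the estimate toward zero. That needs balanced exits and an effect that grows with time, and the documents establish neither.

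**Power is hardly affected.** A comparison with 50 undiluted completers per arm (88%) would suggest a marked loss, but the plan never assumes full retention. Against its own benchmark, the loss is confined to early exits.

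**The unequal-exit case is assumed.** The exit rates and the 1 kg loss are not in the documents. Because baseline DXA follows a four-week run-in on the same exercise, part of any shared loss may already have occurred. The shifts are also smaller than one standard error. The example shows that either direction is possible, not that either is likely.

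**No target for leavers is stated.** The plan does not say whether they should be analysed as if they had continued. Calling the result diluted takes the 12-week change named in SAP 5.1 as the target.

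**Conclusion.** The concern holds as a bias and specification problem in the primary analysis. One of the two permitted missing-data methods turns an exit scan from any week into the week-12 value, and the other leaves its role open. With all of the planned 20% scanned at exit, balanced exits and linear build-up, 0.79 kg becomes 0.66 to 0.75 kg for mean exit at weeks 2 to 9, and 0.71 kg at week 6. Fewer exit scans mean a smaller contribution from this route. With unequal exits and a shared loss, the bias may go either way (0.57 or 0.85 kg in the example). Power falls to about 75% to 78% only for mean exit at weeks 2 to 4.

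The sponsor should correct this before unblinding. It does not make the trial uninterpretable.

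**What to change.** Add to SAP 5.1 and 7, before unblinding:

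- Only DXA scans within 84 ± 3 days, or a stated wider window, are week-12 values.
- Other exit evaluations are recorded as an early-termination visit with their actual study day. They are not entered as Visit 4 and not carried forward.
- Multiple imputation, not LOCF, is the primary method for a missing week-12 value, with the exit value and its study day as auxiliary data.
- A sensitivity analysis may use the exit scan as observed.
- The same rule applies to the other outcomes measured at exit.

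The first two items must not be adopted without the third. If exit scans are barred from being carried forward while LOCF stays, baseline is carried instead and the dilution rises to 20%.

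Protocol 7.5 and 11.2.2 must be reconciled on whether leavers are assessed at exit or attend the remaining visits.

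The cost is a few lines in the SAP and an early-termination visit label in the eCRF, with no added visits, scans or participants. The downside is a slightly larger standard error, because out-of-window scans no longer count as direct observations of the endpoint.
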